This CIP describes the 27G vs larger gauge clinical investigation and provides information about procedures for entering participants. Every care was taken in its drafting, but corrections or amendments may be necessary. These will be circulated to investigators in the clinical investigation. Problems relating to this clinical investigation should be referred, in the first instance, to the Principal Investigator.

This clinical investigation will adhere to the principles outlined in the ISO 14155:2011. It will be conducted in compliance with the CIP, the Data Protection Act and other regulatory requirements as appropriate.

1. AMENDMENT HISTORY

Amendment No.	CIP Version No.	Date Issued	Author(s) of Changes	Details of Changes

2. LIST OF APPENDICES

Appendix A	Assessment of eye reddishness – Reference photographs	
Appendix B	Investigator's Brochure	
Appendix C	Case Report Form	
Appendix D	Case Report Form (S)AEs reporting	
Appendix E	Inform Consent Form	

3. ABBREVIATIONS

AE	Adverse Event
CIP	Clinical Investigation Plan
CRA	Clinical Research Associate
CRF	Case Report Form
EC	Ethics Committee
GCP	Good Clinical Practise
IB	Investigator Brochure
ICF	Informed Consent Form
PI	Principle Investigator
SAE	Serious Adverse Event

4. CLINICAL INVESTIGATION SUMMARY

Title	Comparative study 27G to larger gauge vitrectomy		
Reference Number (Acronym)27G compared to larger gauge sizes			
Clinical Phase	Post-Market stage		
Objectives	To perform a prospective randomized comparison of postoperative recovery between 27G and larger gauge surgical approaches		
Endpoints	Primary endpoint: determine whether ultra-small gauge surgery (27G) improves postoperative outcome and patient morbidity		
Design	Investigator-initiated, comparative double-arm, mono-center, prospective, interventional case study		

Data Collection	Total duration of study for each patient will be 1 week or less (from surgery to last follow-up). See Study Flow Chart 7.3
Planned Clinical investigation Period	2020-2021
Clinical investigation population	Patients that are scheduled for a vitrectomy surgery for either floater removal or macular surgery, with or without combined cataract (phaco) surgery.
Number of Participants	Target 500 patients
Inclusion/Exclusion Criteria	 Inclusion criteria Patients aged over 18 No prior vitrectomy surgery in the study eye (for the same eye) No prior inclusion in this trial Scheduled for vitrectomy for floater removal or macular surgery (including macular holes) without endotamponades such as PFCL, Gas or Silicone oil. Air tamponade is allowed. Exclusion criteria Patients with serious heart, lung, liver, or kidney dysfunction Patients with proliferative diabetic retinopathy, endophthalmitis, uveitis, eyes with refraction >+5D or <-8D, or other eye disease that impacts the outcome of vitrectomy surgery Patients with history of drug abuse or alcoholism Patients participating in other drug or medical device clinical trials before screening for this trial Pregnancy, preparation for pregnancy during clinical trial, or breast-feeding Belief by the investigator that a patient's condition would hinder the clinical trial, such as a patient prone to mental stress, loss of control of mood, or depression
Device Name	EVA used in combination with a trocar system, light fiber, vitrectome and laser fiber either in 27G or larger gauge sizes. In case of a combined surgery also a phaco hand piece and phaco needle are used.
Principle Intended Use	All devices are used within their claimed intended use. In general, all devices are intended to be used during ophthalmic surgery.
Manufacturer Name	D.O.R.C. Dutch Ophthalmic Research Center (International) B.V.

5. INTRODUCTION

Vitrectomy surgery was first described by Machemer in 1971 and became more common in the early 1980's ¹. At that time, vitrectomy was performed transscleral after peritomy of the conjunctiva and exposing the sclera to make the vitrectomy incisions. These incisions need suturing at the end of the surgery. The size of the commercially available instruments was 0.91 mm, commonly referred to as "20 gauge".

Gauge	Inches	Equivalent in mm	Gauge	Inches	Equivalent in mm
8	0.16	4.06	27	0.0164	0.417
9	0.144	3.66	28	0.0148	0.376
10	0.128	3.25	29	0.0136	0.345
11	0.116	2.95	30	0.0124	0.315
12	0.104	2.64	31	0.0116	0.295
13	0.092	2.34	32	0.0108	0.274
14	0.08	2.03	33	0.01	0.254
15	0.072	1.83	34	0.0092	0.234
16	0.064	1.63	35	0.0084	0.213
17	0.056	1.42	36	0.0076	0.193
18	0.048	1.22	37	0.0068	0.173
19	0.04	1.02	38	0.006	0.152
20	0.036	0.91	39	0.0052	0.132
21	0.032	0.81	40	0.0048	0.122
22	0.028	0.71	41	0.0044	0.112
23	0.024	0.61	42	0.004	0.102
24	0.022	0.60	43	0.0036	0.091
25	0.02	0.51	44	0.0032	0.081
26	0.018	0.46	45	0.0028	0.071

[figure not shown]
In 2002, the first 25 gauge vitrectomy instruments became available: the TSV-25 system from Bausch & Lomb, introduced into the market by De Juan ². With these instruments, a new surgical approach was introduced: transconjunctival surgery. In this technique, the conjunctival is left untouched, and the vitrectomy surgery is performed through funnel-shaped instrument cannulas, which are retracted from the eye at the end of the surgery. In ideal conditions, these incisions did not require suturing at the end of the surgery. Both the smaller size of the incisions, the transconjunctival approach and omitting the need for sutures at the end reduced markedly the postoperative morbidity for the patient and accelerated recovery after vitrectomy surgery.

However, the TSV-25 system had many disadvantages. Firstly, the inserters of the instrument cannulas lacked sharpness, hence required a huge force on the eye to be inserted. Also, the smaller diameter of the instruments made them very flexible, making the surgery much more difficult. Furthermore, the smaller inner lumen of the vitrectome reduced the flow of vitreous aspiration which increased significantly the duration of the surgery. Finally, the smaller diameter of the endo-illumination instrument reduced extensively the amount of intra-ocular light coming from a (halogen) light source. Personally, I started using the TSV-25 system in 2002 and used it till 2005. Even at the

end of this 3-year period, I was not able to perform more than 5% of my vitrectomy cases with the TSV-25 system, falling back to 20G surgery in all other cases.

Intra-operative view of 20 gauge transscleral surgery (left) and 27 gauge transconjunctival surgery (right).

In 2005, the use of 23 gauge instruments was introduced by Eckardt ³. These instruments allowed the surgeon to perform transconjunctival vitrectomy surgery, but the instruments were a little larger in size and were also technically enhanced to have less flex and improved inner lumen allowing better flow and light throughput. I started using the 23 gauge system in 2005, and after 6 weeks I already performed 50% of my cases using this system. A few years later, we completely abandoned the 20G approach, and performed all cases 23 gauge. In 2009, we published a comparative report between the 20G and 23G approach, clearly indicating better postoperative morbidity in favor of the 23G system⁴. Nevertheless, in spite of improved shape and sharpness of incision blades, suturing of the incisions still remains required in a significant percentage of patients.

More recently, 27 gauge instruments became available ⁵. Although these are even smaller than the TSV-25 instruments introduced 15 years ago, we found that the improved design of these instruments (e.g. twin duty cycle cutters), in combination with improved vitrectomy devices allowing good vacuum and flow rate, and markedly improved light sources (xenon and LED) do allow the surgeon to perform more than half of the cases using this technique. Because of the extremely small size of the incision, suturing is almost never required, the incisions are closed upon the moment when the instruments are retracted from the eye. We also found that the postoperative recovery is spectacular: the day after the surgery, it is often difficult to see which eye was operated.

Size comparison between vitrectomes (left picture) and intra-ocular forceps (right picture). Left to right: 20 gauge – 23 gauge – 25 gauge – 27 gauge

The aim of this study is to objectively measure a possible difference in postoperative outcome after vitrectomy surgery for either floater removal or macular surgery, with or without combined cataract (phaco) surgery either in 27G and a larger gauge size.

At present, in most centers 27G instruments are used besides larger gauge instruments of 23G of 25G. In this clinical trial, in each individual center the use of 27G instruments will be compared to the other instrument size being used in the standard of care. Also, the pre- and postoperative eye care (including medication) that is currently used in each site will be used for all patients included in that center. For statistical analysis, a comparison will be made between both study arms included *in each center*. Using this approach, it will be possible to evaluate the possible benefit of the use of ultra-small instruments compared to the larger gauge being used in different surgical settings.

6. OBJECTIVES

6.1 Primary objective

The primary objective and primary endpoint are shown in the table below:

Primary objective	Primary endpoint
The aim of this study is to perform a prospective randomized comparison of postoperative recovery between the 27G and larger gauge surgical approach. Patients will be randomized to be operated using 27 gauge or a larger	The outcome of the trial is to prospectively determine whether ultra- small gauge surgery (27G) improves postoperative outcome and patient morbidity.
gauge size.	 For this purpose, the following postoperative parameters will be used: Post-operative redness (Eye Photo) Ophthalmic examination including biomicroscopy to evaluate the amount of intra-ocular inflammation.

The secondary objective and secondary parameters are shown in the table below:

Secondary objective	Secondary endpoint
To obtain additional outcome parameters for both the 27 gauge and larger gauge surgery	Postoperative parameters: - Visual Acuity (LogMAR BCVA) - Intra-ocular pressure (mmHg) - Pain assessment (Questionnaire with visual analogue scale)

7. CLINICAL INVESTIGATION DESIGN

7.1 Trial Design

[figure not shown]
Investigator-initiated, comparative double-arm, mono-center, prospective, interventional case study

50 patients as a target will be enrolled for each site. The study will consist of 3 patient visits. Study follow-up is one week after the vitrectomy surgery.

7.2 Study diagram

7.3 Study Flowchart

	Day 0: Surgery	Day 1 Postoperative (+/- 0 days)	Week 1 Postoperative (+/- 2 days)
Surgery	Х	0	0
Visual Acuity	0	Х	0
Pain assessment	0	Х	0
Intra-Ocular Pressure	0	Х	0
Slit lamp	0	Х	0
Eye photo	0	Х	0
Questionnaire	0	0	Х

8. CLINICAL INVESTIGATION POPULATION

8.1. Number of participants

A total of 500 patients will be included (up to 50 per site).

Enrolment time is 12 months.

8.2. Inclusion criteria

- Patients aged over 18
- No prior vitrectomy surgery in the study eye (for the same eye)
- No prior inclusion in this trial
- Scheduled for vitrectomy for floater removal or macular surgery (including macular holes) without endotamponades such as PFCL, Gas, Silicone oil). (Air tamponade is allowed)

8.3. Exclusion criteria

The participant may not enter the clinical investigation if ANY of the following apply:

- Patients with serious heart, lung, liver, or kidney dysfunction
- Patients with proliferative diabetic retinopathy, endophthalmitis, uveitis, eyes with refraction >+5D or exceeding -8D, or other eye disease that impacts the outcome of vitrectomy surgery
- Patients with HIV
- Patients with history of drug abuse or alcoholism
- Patients participating in other drug or medical device clinical trials before screening for this trial

- Pregnancy, preparation for pregnancy during clinical trial, or breast-feeding
- Belief by the investigator that a patient's condition would hinder the clinical trial, such as a patient prone to mental stress, loss of control of mood, or depression

It should be noted that smoking or vaping is not considered an exclusion criteria.

9. PARTICIPANT SELECTION AND ENROLMENT

9.1. Identifying participants

Patients that are scheduled for vitrectomy surgery that is commonly performed either using 27G or larger gauge instruments will be included.

Similar to the normal clinical path, patients that are referred to the surgical center for either vitreous floaters or macular surgery will be suggested to undergo surgery. After obtaining consent from the patient to be enrolled for surgery, an explanation will be given by the investigator about this clinical trial, and the patient will be invited to participate in the trial. The informed consent will be handed over to the patient at that time to allow to read this through at home. After 1-2 weeks the patient will be called by the study nurse to ask for final approval or disapproval to be enrolled in the trial, and to answer any questions on the trial.

Alternatively, patients that are already waitlisted for vitrectomy for vitreous floaters or macular surgery will be called by the investigator or study nurse to inform them about the ongoing clinical trial. After this informative call, the informed consent form will be mailed to the patient. After 1-2 weeks, the patient will be called again to ask for final approval or disapproval to be enrolled in the trial and to answer any questions, if required.

9.2. Consenting participants

Patients that are scheduled for vitrectomy surgery for either floater removal or macular surgery will be given the informed consent and will be asked to participate in the clinical trial. Per patient, only one eye will be eligible for inclusion in the study.

Following Ethics Committee (EC) approval and before any investigation related procedure, potential participant must personally sign and date the latest approved version of the informed consent form before any clinical investigation specific procedures are performed.

Written and verbal versions of the participant information and Informed consent will be presented to the participants detailing no less than: the exact nature of the clinical investigation; the implications and constraints of the clinical investigation plan; the known side effects and any risks involved in taking part. It will be clearly stated that the participant is free to withdraw from the clinical investigation at any time for any reason without prejudice to future care, and with no obligation to give the reason for withdrawal.

The participant will be allowed as much time as wished to consider the information, and the opportunity to question the Investigator, their GP or other independent parties to decide whether they will participate in the clinical investigation. Written Informed Consent will then be obtained by means of participant dated signature and dated

signature of the person who presented and obtained the informed consent. The person who obtained the consent must be suitably qualified and experienced, and have been authorised to do so by the Coordinating/Principal Investigator. A copy of the signed Informed Consent will be given to the participants. The original signed form will be retained at the clinical investigation site. See also document "recruitment".

In case of updates of the participant information and Informed consent the participant must personally sign and date the latest approved version of the informed consent form before any further clinical investigation specific procedures are performed.

For this clinical trial, signature for approval from the patient will be obtained at the moment of admittance in the hospital on the day of the surgery.

9.3. Randomisation

A 25:25 patient randomization list will be generated in the eCRF (RedCap) to determine whether the surgery will be performed using 27G or larger gauge instruments. This randomization list will be masked for the surgeon: only prior to the next patient scheduled for surgery, the study arm will be visible for the surgeon since the difference in size will be visible during surgery.

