12.3. Data Management

In this study, an electronic case report form (eCRF) within the RedCap platform will be used for data capture. For each surgical center, a different RedCap database will we created, allowing only access to the corresponding investigator and CRO (in case assigned by the CTC). Hence, there will be no sharing of data between the different surgical centers. Also, the data of the different centers will not be pooled for comparison between the centers, only comparison within each center will be performed (see section statistical analysis). Hence, during the whole trial there will be a strict separation of study data between each center.

All documents will be stored safely in confidential conditions. On all clinical investigationspecific documents, other than the signed consent, the participant will be referred to by the clinical investigation participant number/code, not by name.

All clinical investigation documentation will be kept for 10 years from the clinical investigation plan defined end of clinical investigation point. When the minimum retention period has elapsed, clinical investigation documentation will not be destroyed without permission from the sponsor.

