13.2. The number of participants

We estimated the number of participants by calculating the number of participants needed for the three chosen outcomes (bio cellen, bio tyndall and redness of the eye), based on the pilot data. The target p-value was 0.5/3 (=0.0167) in order to correct for multiple testing, and the power was set to 80%. Because we want to see a difference on the three outcomes, we choose the highest sample size estimation, based on the work of Zaho, Rahardja & Yongming (2008), who proposed sample size estimators ordinal data using the Wilcoxon-Mann-Whitney test and available in the R package *sample size*. The percentages for each categories of the ordinal variables by group are used as input for the sample size estimations. The next table presents the results obtained.

	Total by group	Total individuals
Bio cellen	428	858
Bio tyndall	430	860
Redness eye	27	54

Based on this table, a total of 860 patients would be required by group in order to show a difference between 23G and 27G on the three parameters of the outcome: bio tyndall, bio cellen and redness eye.

For each surgical site 25 patients will be recruited by group (i.e. 50 patients will be included at each site).

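### A 25:25 list per site, with every arm seen by the surgeon, makes late assignments partly guessable if the list is unblocked, the site fills and counts are shared: about 70% correct in the last 10 patients

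*Combined protocol and SAP*

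**What the plan says.** Section 9.3 sets the allocation: "A 25:25 patient randomization list will be generated in the eCRF (RedCap) to determine whether the surgery will be performed using 27G or larger gauge". The list is masked ahead of time, but just before each operation "the study arm will be visible for the surgeon since the difference in size will be visible during surgery". No block size, stratification factor or other restriction is given.

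Section 13.2 repeats the fixed split: "For each surgical site 25 patients will be recruited by group (i.e. 50 patients will be included at each site"). Section 7.1 calls this a target ("50 patients as a target will be enrolled for each site"), and section 8.1 treats it as a ceiling: "A total of 500 patients will be included (up to 50 per site").

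Section 12.3 separates the sites: for each centre "a different RedCap database will we created, allowing only access to the corresponding investigator and CRO (in case assigned by the CTC"). The 25:25 list is therefore read here as specific to one site. The plan does not say who generates the list, or whether the investigator's access excludes it.

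Two provisions bear on what can still happen before a patient is entered. One exclusion in section 8.3 rests on judgement: "Belief by the investigator that a patient's condition would hinder the clinical trial". Under section 9.2, "signature for approval from the patient will be obtained at the moment of admittance in the hospital on the day of the surgery".

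**The concern.** Masking the next entry protects allocation only if earlier entries do not give it away. In a closed set with equal totals they do. Whoever knows how many of each arm have been used knows what remains, and once one arm reaches 25 the rest is known. The surgeon cannot be blinded to gauge, so the tally is available without opening the list.

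If someone could both guess the arm and influence entry, easier or harder eyes could be directed towards one arm. Redness, cells and flare would then differ for reasons unrelated to gauge. The primary Wilcoxon-Mann-Whitney tests in section 13.1 carry no covariates, so such a case-mix difference would pass into the comparison. Independent grading of the redness photographs (section 11.2) and inclusion of all randomised patients (section 13.7) act after entry and do not touch this.

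**Working it through.** **Inputs.** 25 per arm and 50 per site (sections 9.3 and 13.2); a maximum of 50 per site and 500 in total (section 8.1), so 500/50 = 10 full sites; every past arm known to the surgeon (section 9.3). Assumed, because the plan is silent: one unblocked random permutation per site, all 50 places used, and counts held by one surgeon or shared. The plan gives no predictability figure to reproduce.

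**1. Chance of a correct guess.** The guesser names the arm used less so far. After k assignments,

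P(correct) = Σₐ [C(25,a)·C(25,k−a)/C(50,k)] × max(25−a, 25−k+a)/(50−k).

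- Patient 1: 50.0%. Patient 41: 61.0%. Patients 46–47: 68.0%. Patients 48–49: 74.5%. Patient 50: 100%.
- Averages: first 40, 54.9%; last 10, 70.0%; last 5, 77.0%; all 50, 57.9%.
- Closed-form check: expected excess over 25 correct = 2⁴⁹/C(50,25) − 0.5 = 3.95, so 28.95 of 50. Simulation of the last 10 also gives 70.0%.

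**2. Determined assignments.** Expected length of the fully determined tail = 2×25/26 = 1.92 patients. P(at least the last 2 determined) = 49%; P(at least the last 3) = 23%.

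**3. Sensitivity to the assumptions.**
- A site stopping at 40: 58.6% in its last 10, and no certain assignment.
- Several surgeons who do not share counts: between 50% and 70% in the last 10.
- Small blocks of known size instead: size 4 gives (0.500 + 0.667 + 0.667 + 1.000)/4 = 70.8% over the whole list; size 6 gives 68.3%.

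**4. From guessing to bias.** Suppose case mix moves by s SD in the guessed direction: +s when 27G is guessed, −s when the larger gauge is guessed, 0 when the tally is tied. The expected false difference is then (2×28.95 − 50)/25 × s = 0.316s.

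Not all of this comes from the forced total. Under coin-flip allocation, where guessing succeeds 50% of the time, the same rule gives 0.148s in simulation, because the guesses are correlated with the realised arm sizes. The part attributable to the forced total is 0.316 − 0.148 = 0.168, or about 0.17s. As a second view, if steering occurs only when the next-arm probability is at least 2/3 (about 7 of 50 patients), the multiplier is again about 0.17.

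- s = 0.25 SD (assumed): 0.168 × 0.25 = 0.04 SD.
- s = 0.1 to 0.5 SD: 0.02 to 0.08 SD.

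**5. Scale.** Section 13.2 uses p = 0.0167 and 80% power. A normal approximation to the detectable effect is (2.394 + 0.842) × √(2/n):

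- Flare, n = 430 per group: 0.22 SD; 0.042/0.221 = 19%.
- Redness, n = 27 per group: 0.88 SD; 0.042/0.881 = 5%.

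These are rough conversions. The outcomes are ordinal and the pilot percentages are not given.

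**6. A longer list.** A 40:40 list stopped at 50 gives, by simulation, 53.0% correct overall, 55% in the last 10 and essentially no determined assignments. The multiplier is 0.194s under the first steering rule and about 0.003s when steering needs a next-arm probability of at least 2/3. Mean variance inflation is 1.008.

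**The case against.** The strongest case against has four parts.

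*The routes to selection are narrow.* The examples attached to the judgement exclusion in section 8.3 concern temperament, not easy or difficult eyes. Under section 9.1 patients are invited, and then telephoned for a decision, 1–2 weeks or more before surgery. What remains is late refusal or reordering of cases, and the plan describes neither. This stands, and it limits the concern. It does not close the gap, because entry is completed by a signature on the day of surgery.

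*Certainty is conditional.* A reader might infer that the final assignment at every site is known in advance. The documents do not support that: 50 is a target and a ceiling, block structure is unstated, and nothing says that surgeons share counts.

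*The bias is easily overstated.* A reader might take the whole 0.316s, or 0.08 SD at a 0.25 SD shift (36% of 0.22 SD), as the effect of the list. Nearly half of it (0.148/0.316 = 47%) would arise with coin-flip allocation. The shift itself is also generous: ±0.25 SD is a 0.5 SD swing, applied whenever the tally is not tied. Within one site of 25 per arm the standard error is √(2/25) = 0.28 SD, so a 0.04 SD bias moves a 5% two-sided error rate only to about 5.2%. A bias in the same direction at several sites would matter more in the complementary mixed models of section 13.1, but section 13 makes the within-site comparison the analysis.

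*A fixed 1:1 list per site is an ordinary choice* where the operator cannot be masked, and it is less guessable than small blocks. True. But a longer list is less guessable still and costs almost nothing.

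**Conclusion.** The point holds as a conditional weakness of minor to moderate severity. With one unblocked list, a full site and shared counts, about 4 extra guesses in 50 are correct, mostly near the end: 58% overall, 70% in the last 10 and about 1.9 determined assignments. If any of these conditions fails, the figures change. Early stopping or unshared counts lower them; small blocks of known size raise them.

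The bias attributable to the forced total is about 0.17 times the steering shift, or 0.04 SD at an assumed 0.25 SD. That is a noticeable fraction of the effect implied for flare (19%) and a small one for redness (5%). No figure in the documents supports any particular steering size.

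The stronger reading, that selection is taking place or that the comparison is already compromised, is not supported. The plan shows an opportunity, with limited means of using it.

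**What to change.** In section 9.3, state how the list is generated. For each site use a 1:1 list longer than the site target, for example 40:40 (80 entries), and stop the site at 50 patients whatever the split. In section 13.2, change 25 patients per group to about 25.

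State that the list is prepared and loaded by someone outside the site, such as the trial statistician. In section 12.3, exclude the list from the investigator's REDCap access.

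Do not substitute small permuted blocks. They are more guessable when every arm is seen.

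The longer list reduces the opportunity and does not abolish it: under the first steering rule it removes (0.316 − 0.194)/0.168 = 73% of the part attributable to the forced total.

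The cost is a few sentences and a longer list in the same eCRF, with no extra patients, staff or procedures. Site arms may end slightly unequal. A 23 v 27 split, for instance, has variance (1/23 + 1/27)/(2/25) = 1.006 times that of 25 v 25, and the average increase is about 1%. The planned Wilcoxon-Mann-Whitney test does not need equal arms.
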